5 SELECTION OF SUBJECTS

5.1 INCLUSION CRITERIA

Eligible subjects will be considered for inclusion in this study if they meet all of the following criteria:

1. Men and women ≥ 18 years of age.
2. ECOG performance status of 0 to 2.
3. Diagnosis of CLL that meets published diagnostic criteria ([Hallek 2008](#)):
 - a. Monoclonal B-cells (either kappa or lambda light chain restricted) that are clonally co-expressing ≥ 1 B-cell marker (CD19, CD20, or CD23) and CD5.
 - b. Prolymphocytes may comprise $\leq 55\%$ of blood lymphocytes.
 - c. Presence of $\geq 5 \times 10^9$ B lymphocytes/L (5000 μL) in the peripheral blood (at any point since diagnosis); this applies to CLL only.
4. Must have ≥ 1 of the following high-risk prognostic factors:
 - a. Presence of 17p del by central laboratory.
 - b. Presence of 11q del by central laboratory.
5. Active disease meeting ≥ 1 of the following IWCLL 2008 criteria for requiring treatment:
 - a. Evidence of progressive marrow failure as manifested by the development of, or worsening of, anemia (hemoglobin < 10 g/dL) and/or thrombocytopenia (platelets $< 100,000/\mu\text{L}$).
 - b. Massive (ie, ≥ 6 cm below the left costal margin), progressive, or symptomatic splenomegaly
 - c. Massive nodes (ie, ≥ 10 cm in the longest diameter), progressive, or symptomatic lymphadenopathy.
 - d. Progressive lymphocytosis with an increase of $> 50\%$ over a 2-month period or a LDT of < 6 months. LDT may be obtained by linear regression extrapolation of ALC obtained at intervals of 2 weeks over an observation period of 2 to 3 months. In subjects with initial blood lymphocyte counts of $< 30 \times 10^9/\text{L}$ (30,000/ μL), LDT should not be used as a single parameter to define indication for treatment. In addition, factors contributing to lymphocytosis or lymphadenopathy other than CLL (eg, infections) should be excluded.
 - e. Autoimmune anemia and/or thrombocytopenia that is poorly responsive to standard therapy.
 - f. Constitutional symptoms documented in the subject's chart with supportive objective measures, as appropriate, defined as ≥ 1 of the following disease-related symptoms or signs:
 - i. Unintentional weight loss $\geq 10\%$ within the previous 6 months before Screening.
 - ii. Significant fatigue (ie, ECOG performance status 2 or worse; inability to work or perform usual activities).

- iii. Fevers > 100.5°F or 38.0°C for ≥ 2 weeks before Screening without evidence of infection.
 - iv. Night sweats for > 1 month before Screening without evidence of infection.
6. Must have received ≥ 1 prior therapies for CLL.
8. Meet the following laboratory parameters:
 - a. ANC ≥ 750 cells/μL ($0.75 \times 10^9/L$) or ≥ 500 cells/μL ($0.50 \times 10^9/L$) in subjects with documented bone marrow involvement, and independent of growth factor support 7 days before assessment.
 - b. Platelet count ≥ 30,000 cells/μL ($30 \times 10^9/L$) without transfusion support 7 days before assessment. Subjects with transfusion-dependent thrombocytopenia are excluded.
 - c. Serum AST/SGOT and ALT/SGPT ≤ 3.0 x ULN.
 - d. Total bilirubin ≤ 1.5 x ULN.
 - e. Estimated creatinine clearance (ie, eGFR using Cockcroft-Gault) ≥ 30 mL/min.
9. Able to receive all outpatient treatment, all laboratory monitoring, and all radiologic evaluations at the institution that administers study drug for the entire study.
10. Women who are sexually active and can bear children must agree to use highly effective forms of contraception while on the study and for 2 days after the last dose of acalabrutinib or 90 days after the last dose of ibrutinib, whichever is longer. Highly effective forms of contraception are defined in [Section 6.2.11](#).
11. Men who are sexually active and can beget children must agree to use highly effective forms of contraception during the study and for 2 days after the last dose of acalabrutinib or 90 days after the last dose of ibrutinib, whichever is longer. Highly effective forms of contraception are defined in [Section 6.2.11](#).
12. Men must agree to refrain from sperm donation during the study and for 2 days after the last dose of acalabrutinib or 90 days after the last dose of ibrutinib, whichever is longer.
13. Must be willing and able to adhere to the study visit schedule, understand and comply with other protocol requirements, and provide written informed consent and authorization to use protected health information (in accordance with national and local patient privacy regulations). Note vulnerable subjects, as defined in the International Conference on Harmonisation (ICH) GCP, are not allowed on this protocol (eg, prisoners or institutionalized subjects).

5.2 EXCLUSION CRITERIA

Subjects will be ineligible for this study if they meet any of the following criteria:

1. Known CNS lymphoma or leukemia.
2. Known prolymphocytic leukemia or history of, or currently suspected, Richter's syndrome.
3. Uncontrolled AIHA or ITP defined as declining hemoglobin or platelet count secondary to autoimmune destruction within the screening period or requirement for high doses of steroids (> 20 mg daily of prednisone daily or equivalent).

4. Prior exposure to ibrutinib or to a BCR inhibitor (eg Btk or PI3 kinase or Syk inhibitors) or a BCL-2 inhibitor (eg, ABT-199).
5. Received any chemotherapy, external beam radiation therapy, anticancer antibodies, or investigational drug within 30 days before first dose of study drug.
6. Corticosteroid use > 20 mg within 1 week before first dose of study drug, except as indicated for other medical conditions such as inhaled steroid for asthma, topical steroid use, or as premedication for administration of study drug or contrast. For example, subjects requiring steroids at daily doses > 20 mg prednisone equivalent systemic exposure daily, or those who are administered steroids for leukemia control or white blood cell count lowering are excluded.
7. Prior radio- or toxin-conjugated antibody therapy.
8. Prior allogeneic stem cell or autologous transplant.
9. Major surgery within 4 weeks before first dose of study drug.
10. History of prior malignancy except for the following:
 - a. Malignancy treated with curative intent and with no evidence of active disease present for more than 3 years before Screening and felt to be at low risk for recurrence by treating physician.
 - b. Adequately treated lentigo maligna melanoma without current evidence of disease or adequately controlled non-melanomatous skin cancer
 - c. Adequately treated cervical carcinoma in situ without current evidence of disease
11. Significant cardiovascular disease such as uncontrolled or symptomatic arrhythmias, congestive heart failure, or myocardial infarction within 6 months of screening, or any Class 3 or 4 cardiac disease as defined by the New York Heart Association Functional Classification, or QTc > 480 msec at screening.
12. Unable to swallow capsules or malabsorption syndrome, disease significantly affecting gastrointestinal function, or resection of the stomach or small bowel or gastric bypass, symptomatic inflammatory bowel disease, or partial or complete bowel obstruction.
13. Uncontrolled active systemic fungal, bacterial, viral, or other infection (defined as exhibiting ongoing signs/symptoms related to the infection and without improvement, despite appropriate antibiotics or other treatment) or ongoing intravenous anti-infective treatment.
14. Known history of infection with HIV.
15. Serologic status reflecting active hepatitis B or C infection. Subjects with hepatitis B core antibody positive who are surface antigen negative or who are hepatitis C antibody positive will need to have a negative polymerase chain reaction (PCR) result before randomization. Those who are hepatitis B surface antigen positive or hepatitis B PCR positive and those who are hepatitis C PCR positive will be excluded.
16. History of stroke or intracranial hemorrhage within 6 months before randomization.
17. History of bleeding diathesis (eg, hemophilia, von Willebrand disease).
18. Requires or receiving anticoagulation with warfarin or equivalent vitamin K antagonists (eg, phenprocoumon) within 7 days of first dose of study drug.
19. Requires treatment with a strong CYP3A inhibitor/inducer.

20. Requires treatment with proton-pump inhibitors (eg, omeprazole, esomeprazole, lansoprazole, dexlansoprazole, rabeprazole, or pantoprazole).
21. Breastfeeding or pregnant.
22. Concurrent participation in another therapeutic clinical trial.
23. Presence of a gastrointestinal ulcer diagnosed by endoscopy within 3 months before screening

6 DOSAGE AND ADMINISTRATION

6.1 IDENTIFICATION OF INVESTIGATIONAL PRODUCT

6.1.1 Acalabrutinib

Acalabrutinib is provided as hard gelatin capsules for oral administration. The capsules are packaged in opaque high-density polyethylene (HDPE) plastic bottles with labels bearing the appropriate label text as required by governing regulatory agencies. The drug product is manufactured for Acerta Pharma by a contract manufacturer. All formulation excipients are compendial and are commonly used in oral formulations.

Refer to the Investigator Brochure for additional information regarding the drug product to be used in this study.

6.1.2 IMBRUVICA (Ibrutinib)

This study will use commercially available ibrutinib. The Sponsor will either directly supply sites with ibrutinib or the sites will be reimbursed to prescribe ibrutinib; this will be detailed separately in each site's clinical trial agreement.

Ibrutinib is provided as 140-mg capsules *or tablets*. Refer to IMBRUVICA approved label for details.

6.2 DRUG PREPARATION AND ADMINISTRATION

6.2.1 Acalabrutinib

Investigators are prohibited from supplying acalabrutinib to any subjects not properly enrolled in this study. The investigator must ensure that subjects receive acalabrutinib only from personnel who fully understand the procedures for administering the drug.

Acalabrutinib is intended to be administered orally BID (with the second daily dose 11 to 13 hours after first dose) with 8 ounces (approximately 240 mL) of water. The capsules should be swallowed intact and subjects should not attempt to open capsules or dissolve them in liquid.

If a dose is missed, it can be taken up to 3 hours after the scheduled time with a return to the normal schedule for the next dose. If it has been > 3 hours, the dose should not be taken and the subject should take the next dose at the scheduled time. The missed dose will not be made up and must be returned to the site at the next scheduled visit.

6.2.2 Assessment of Toxicity

The evaluation of potential treatment-induced toxicity in subjects with advanced CLL may be quite difficult requiring careful consideration of the manifestations of the underlying disease, as well as adverse reactions to the therapy under study. Some of the conventional criteria for toxicity are not applicable especially under circumstances of progressive bone marrow failure from the CLL itself. Dose modifications for hematologic toxicity in subjects with CLL must consider the increased frequency of hematologic compromise at the initiation of therapy. Therefore the standard criteria used for solid tumors are difficult to be applied directly; many subjects would be considered to have Grade 2 to 4 hematologic toxicity at presentation.

As a consequence, dose modification decisions for subjects with cytopenia (below the lower limit of the normal range) at baseline will be based on the IWCLL 2008 grading scale for hematologic toxicity in CLL studies (see [Appendix E](#)).

For dose modifications or discontinuation guidance of acalabrutinib in Arm A, see [Section 6.2.4](#). For dose modifications or discontinuation guidance of ibrutinib in Arm B, see [Section 6.2.9](#).

6.2.3 Dose Delays for Acalabrutinib

Treatment with acalabrutinib should be held for any unmanageable, potentially study drug-related toxicity that is Grade ≥ 3 in severity. Any other clinically important events where dose delays may be considered appropriate by the investigator must be discussed with the Medical Monitor. Study drug may be held for a maximum of 28 consecutive days from expected dose due to toxicity. Study treatment should be discontinued in the event of a toxicity lasting > 28 days, unless reviewed and approved by the Medical Monitor.

Note: temporary withholding of study drug for as little as 7 days can cause a transient worsening of disease and/or of constitutional symptoms. Refer to [Section 8.1](#) for more information on assessing disease progression under these circumstances.

6.2.4 Dose Modification and Discontinuation for Acalabrutinib

Treatment-related Lymphocytosis

Treatment-related lymphocytosis is defined as ALC > 5000/ μ L and an increase above baseline, and is associated with agents known to inhibit BCR ([Hallek 2008](#), [NCCN Version 1.2016](#),

[Cheson 2012](#)). Given the known mechanism of action of BCR-inhibiting agents including ibrutinib, treatment-related lymphocytosis is an expected and frequent phenomenon observed with initiation (or re-initiation) of Btk inhibitors. Specifically, the IMBRUVICA approved label states an increase in lymphocyte counts ($\geq 50\%$ increase from baseline and above absolute lymphocyte count of $5,000/\mu\text{L}$) occurred in 77% of subjects (N=195) in the pivotal Phase 3 CLL study. The onset of lymphocytosis occurred during the first month of ibrutinib therapy and resolved by a median of 23 weeks (range: 1 to 104+ weeks). Asymptomatic treatment-related lymphocytosis should not be considered an AE and subjects should remain on study treatment. A high number of circulating malignant cells ($\geq 400,000/\mu\text{L}$) may confer increased risk; these subjects should be closely monitored. Administer supportive care such as hydration and/or leukaphoresis as indicated. Acalabrutinib may be temporarily held and the Medical Monitor should be contacted.

The actions in [Table 6-1](#) should be taken for the following toxicities:

- Grade 4 ANC ($< 500/\mu\text{L}$) for > 7 days (Neutrophil growth factors are permitted per ASCO guidelines [[Smith 2015](#)] and use must be recorded on the case report form [CRF]).
- Grade 3 platelet decreases in presence of significant bleeding.
- Grade 4 platelet decreases.
- Grade 3 or 4 nausea, vomiting, or diarrhea, if persistent despite optimal antiemetic and/or anti-diarrheal therapy.
- Any other Grade 4 toxicity or unmanageable Grade 3 toxicity.

Table 6-1. Drug Discontinuation Actions for Acalabrutinib

Occurrence	Action
1st - 2nd	Hold acalabrutinib until recovery to Grade ≤ 1 or baseline; may restart at original dose level
3rd	Hold acalabrutinib until recovery to Grade ≤ 1 or baseline; restart at one dose level lower (100 mg once daily)
4th	Discontinue acalabrutinib

Any changes to the dosing regimen must be recorded in the Dosage Administration CRF.

If acalabrutinib is reduced for apparent treatment-related toxicity, the dose need not be re-escalated, even if there is minimal or no toxicity with the reduced dose. However, if the subject tolerates a reduced dose of acalabrutinib for ≥ 4 weeks then the dose may be increased to the next higher dose level, at the discretion of the investigator. Such re-escalation may be

particularly warranted if further evaluation reveals that the AE that led to the dose reduction was not treatment-related. However, the maximum dose of acalabrutinib is 100 mg BID for this protocol.

Any changes to the dosing regimen must be recorded in the Dosage Administration CRF.

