1.3 CLINICAL STUDIES

1.3.1 Pharmacokinetics and Pharmacodynamics of Acalabrutinib

ACE-HV-001 was a PK/pharmacodynamic (PD), dose-ranging, food-effect, and drug-drug interaction study evaluating BID and QD dosing for 1 or 2 days in healthy volunteers. This study evaluated the PK/PD of acalabrutinib at various dose levels and regimens. The starting dose for acalabrutinib was 2.5 mg BID. This study has been completed and no adverse laboratory, vital signs, or ECG findings were observed (2.5 to 50 mg BID; 50 to 100 mg QD). Three AEs related to study drug were reported. Each AE was Grade 1 and resolved without treatment. The AEs were constipation (2.5 mg BID), feeling cold (75 mg QD), and somnolence (75 mg QD).

In Part 1, PK properties of acalabrutinib were evaluated after oral administration of 2 daily divided doses of 2.5 to 50 mg and a single dose of 100 mg. Of the 30 subjects evaluated, all observed systemic concentrations of acalabrutinib. Acalabrutinib plasma time to maximum concentration (T_{max}) values were between 0.5 and 1.0 hour for all dose cohorts and were independent of dose level. The increase in mean maximum observed drug concentration (C_{max}) values was greater than dose proportional based on the increases of C_{max} from the first dose administered. When evaluating AUC_{0-12} , AUC_{0-24} or AUC_{0-inf} , the mean values increased in a dose proportional manner based on the increases of the total dose administered. Mean half-life ($t_{1/2}$) values ranged from 0.97 to 2.1 hours, and appeared to decrease as the dose increased. The mean calculated oral clearance (CL/F: 165 to 219 L/h) and volume of distribution values (V_z/F : 233 to 612 L) appeared to be independent of the dose administered.

Acalabrutinib was not detected in the urine of subjects receiving the 2.5- or 5.0-mg BID doses of acalabrutinib. Acalabrutinib was detected in urine of other subjects (0.4% to 0.6% of dose) and amounts increased in a dose-dependent manner.

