6.3.2 Guideline for Use of CYP Inhibiting/Inducing Drugs

Acalabrutinib

At the systemic exposure levels expected in this study, acalabrutinib inhibition of CYP-mediated metabolism of other drugs is not anticipated. However, acalabrutinib is metabolized in part by CYP3A. In a clinical drug-drug interaction study, co-administration of the potent CYP3A inhibitor, itraconazole, increased the mean plasma exposures of acalabrutinib by about 5-fold (Section 1.3.1). In addition, concomitant administration of a strong inducer of CYP3A, rifampicin, reduced the exposure of acalabrutinib to 23%, relative to acalabrutinib dosed alone. Concomitant administration of strong CYP3A inhibitors/inducers and acalabrutinib should be avoided when possible (see Appendix C for a list of these agents). *Subjects requiring long-term (>1 week) treatment with a strong CYP3A inhibitor/inducer are excluded from the study. In addition, the use of strong CYP3A inhibitors or inducers within 7 days of the first dose of study drug is prohibited. If a subject requires short-term treatment (≤7 days) with a strong CYP3A inhibitor, acalabrutinib treatment should be interrupted. If the subject requires treatment with a moderate CYP3A inhibitor, the acalabrutinib dose should be reduced to 100 mg QD. Co-administration of strong CYP3A inducers should be avoided. If a subject requires treatment with a strong CYP3A inducer, the acalabrutinib dose should be increased to 200 mg BID.*

Ibrutinib

Refer to the section titled “Dose Modifications for Use with CYP3A Inhibitors” in the IMBRUVICA approved label.

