6.3.4 Prohibited Concomitant Medications

Any chemotherapy, anticancer immunotherapy, experimental therapy, or radiotherapy for treating CLL are prohibited if being used to treat the disease initially under study. Short course use of steroids (≤ 2 weeks) > 20 mg/day is permitted for premedication use, or to manage infusion related reactions or to manage other inflammatory reactions, such as asthma exacerbations. High-dose corticosteroids used to treat the underlying CLL are not allowed on study. Localized, short courses of radiotherapy are allowed for the treatment of lesions unrelated to the disease under study, if approved by the medical monitor. Should a subject develop a second primary malignancy while on trial, continuation on trial medication after curative treatment of the second primary malignancy may be considered after discussion with the medical monitor.

Warfarin or equivalent vitamin K antagonists (eg, phenprocoumon) are prohibited.

The concomitant use of strong inhibitors/inducers of CYP3A (see [Appendix C](#)) should be avoided when possible (see [Section 6.3.2](#)). Concomitant administration of a strong inducer of CYP3A has the potential to decrease exposure of acalabrutinib and could reduce efficacy. For additional information on drugs with potential drug-drug interactions, refer to [Section 6.3](#).

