7.2.2.6 Overdose Instructions

In the event of ingestion of more than the recommended dosage per protocol, additional clinical monitoring is recommended by the sponsor. For any subject experiencing an acalabrutinib or ibrutinib overdose (ingestion of more than the recommended dosage), observation for any symptomatic side effects should be instituted, and vital signs, biochemical and hematologic parameters should be followed closely (consistent with the protocol or more frequently, as needed). Appropriate supportive management to mitigate adverse effects should be initiated. If the overdose ingestion of acalabrutinib or ibrutinib is recent and substantial, and if there are no medical contraindications, use of gastric lavage or induction of emesis may be considered.

The medical monitor must be contacted if a study drug overdose occurs.

7.2.2.7 Expedited Reporting Requirements for Serious Adverse Events/Adverse Events of Special Interest

All SAEs/AES/s must be reported within 24 hours of discovery. All initial SAE/AES/s reports and follow-up information will be reported using the protocol-specific electronic data capture system. If electronic SAE/AES/s reporting is not available, paper SAE/AES/s report forms must be sent to the AstraZeneca Representative, or designee. The AstraZeneca Representative may request follow-up and other additional information from the investigator (eg, hospital admission/discharge notes and laboratory results).

Whenever possible, SAEs/AES/s should be reported by diagnosis term not as a constellation of symptoms. All deaths should be reported with the primary cause of death as the AE term, as death is typically the outcome of the event, not the event itself. The primary cause of death on the autopsy report should be the term reported. Autopsy and postmortem reports must be forwarded to the AstraZeneca Representative, or designee, as outlined above.

If study drug is discontinued because of an SAE/AES/s, this information must be included in the SAE/AES/s report.

An SAE/AES/s may qualify for mandatory expedited reporting to regulatory authorities if the SAE/AES/s is attributable to the study drug and is not listed in the current Investigator Brochure (ie, an unexpected event). In this case, Acerta Pharma will forward a formal notification describing the suspected unexpected serious adverse reaction (SUSAR) to all investigators. Each investigator must then notify his or her IRB/IEC of the SUSAR.

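### For an acalabrutinib subject who needs a strong CYP3A inducer, Protocol 6.2.4 caps the dose at 100 mg BID and Protocol 6.3.2 directs 200 mg BID, with no cross-reference between them

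*Protocol*

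**What the plan says.** Section 6.2.4 of the Protocol (dose modification and discontinuation for acalabrutinib) covers treatment-related lymphocytosis, holds and reductions for toxicity (Table 6-1), and re-escalation after a reduction. The re-escalation paragraph closes with: "However, the maximum dose of acalabrutinib is 100 mg BID for this protocol".

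Section 6.3.2 (CYP inhibiting and inducing drugs) first discourages the combination: "Concomitant administration of strong CYP3A inhibitors/inducers and acalabrutinib should be avoided when possible". It reports that rifampicin, a strong inducer, "reduced the exposure of acalabrutinib to 23%, relative to acalabrutinib dosed alone". It then gives a dose for the case where the combination cannot be avoided: "If a subject requires treatment with a strong CYP3A inducer, the acalabrutinib dose should be increased to 200 mg BID".

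Other sections touch on the same situation:

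- Section 5.2, exclusion criterion 19, keeps out a subject who "Requires treatment with a strong CYP3A inhibitor/inducer". Section 6.3.2 adds that a need lasting more than 1 week is excluding, and it bars use within 7 days of the first dose.
- Section 6.3.4, although headed as prohibited medications, only asks that strong inducers be avoided where possible. It warns: "Concomitant administration of a strong inducer of CYP3A has the potential to decrease exposure of acalabrutinib and could reduce efficacy".
- Section 7.2.2.6 sets out overdose handling, which applies "In the event of ingestion of more than the recommended dosage per protocol".
- The Synopsis and Section 4 give 100 mg BID as the Arm A dose, with no exception.

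**The concern.** Each section, read alone, gives a clear answer, and the answers differ. A site that starts from Section 6.2.2 is sent to 6.2.4 for Arm A dose modification and meets a ceiling of 100 mg BID. A site that starts from Section 1.2.7 or 6.3.4 is sent to Section 6.3 or 6.3.2 and meets 200 mg BID. Two sites with the same kind of subject could therefore give daily doses that differ two-fold, each relying on current protocol text.

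The protocol itself says that a strong inducer lowers exposure and could reduce efficacy, so the choice matters to the individual subject. The status of the higher dose is also unsettled. If the ceiling is general, 200 mg BID looks like a deviation and might fall under the overdose section, which requires contact with the medical monitor. If the ceiling concerns re-escalation only, 200 mg BID is simply what the protocol directs.

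**Working it through.** **1. Do the two statements conflict?**

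| | Section 6.2.4 | Section 6.3.2 |
|---|---|---|
| Dose | at most 100 mg BID | increase to 200 mg BID |
| Daily total | 2 × 100 = 200 mg | 2 × 200 = 400 mg |
| Stated scope | the whole protocol, no exception | subject requiring a strong CYP3A inducer |
| Refers to the other section? | no | no (only to Section 1.3.1, Appendix C and the ibrutinib label) |

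Ratio: 400 / 200 = 2.0. On its wording, the 6.3.2 dose exceeds the 6.2.4 maximum.

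**2. Does anything else resolve it?** Sections 4, 6.2.2, 6.3.4, 7.2.2.6 and 8.1, the Synopsis and Appendix K were compared. None states an exception to the ceiling or limits its scope. Section 8.1 adds a possible third outcome, because needing prohibited treatment is a listed reason to stop study drug. Section 6.3.4 does not prohibit strong inducers outright, so that route does not clearly apply.

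**3. Can the situation still arise?** The entry restrictions act at or near the first dose, and the amendment summary notes that the study is no longer enrolling. What remains is a need that develops in a subject still taking acalabrutinib. Section 6.3.2 provides for this, and Appendix K anticipates COVID-19 treatments that are strong CYP3A4 inhibitors or inducers.

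**4. Are the two doses interchangeable in exposure?** Take uninduced exposure at 100 mg BID as 100%, and the protocol's rifampicin figure of 23%.

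- At 100 mg BID with the inducer: 0.23 × 1 = 23%.
- At 200 mg BID with the inducer, assuming dose proportionality: 0.23 × 2 = 46%.

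Proportionality is an assumption. Section 1.3.1 says of AUC that "the mean values increased in a dose proportional manner", but for total doses only up to 100 mg. Section 2.1 suggests a plateau after 250 mg QD and does not describe BID dosing with an inducer. If exposure rose less than proportionally, the second figure would fall below 46%. Its limit of 23% (no gain at all) is a bound, not something the documents report. These figures show only that the instructions differ in effect; they do not favour either.

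**5. What happens to relative dose intensity?** SAP 6.3 fixes the denominator at duration × 100 mg × 2. If a share f of the exposure time is at 200 mg BID and all other dosing is as planned:

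RDI = 100 × [(1 − f) × 200 + f × 400] / 200 = 100 × (1 + f).

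All values of f below are assumptions. Thirty-six months is 36 × 30.4375 = 1095.75 days.

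| Time at 200 mg BID | f | RDI |
|---|---|---|
| 7 days in 36 months | 7 / 1095.75 = 0.0064 | 100.6% |
| 28 days in 36 months | 28 / 1095.75 = 0.0256 | 102.6% |
| 10% of exposure | 0.10 | 110% |
| 25% of exposure | 0.25 | 125% |

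An RDI above 100% does not by itself remove a subject from the per protocol population, where SAP 3.3 excludes only values below 75%.

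**The case against.** The strongest reply is that there is no conflict. Section 6.2.4 never mentions CYP3A. Its ceiling qualifies the sentences on re-escalation after a toxicity reduction, so Section 6.3.2 governs inducers on its own, and a dose it directs is by definition given per protocol and is not an overdose. That reading is possible and may be what was intended. It is not what the text says, because the ceiling is worded for the whole protocol. Table 6-1 also has a single reduced level, 100 mg once daily, so the next level up is already 100 mg BID. If the ceiling concerned re-escalation only, it would add almost nothing, and a site can reasonably read it as general.

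A second reply is that the situation is rare and the statistical consequences are negligible. That stands. The entry criteria and the advice to avoid inducers should keep numbers small, no affected subject is reported in the documents, and the RDI scenarios of 28 days and longer exceed the 1-week limit in Section 6.3.2. That limit is worded as eligibility, so longer on-study use is not ruled out, but a 7-day course moves RDI by only 0.6 percentage points. The point therefore rests on the dosing contradiction, not on the RDI or exposure arithmetic. The overdose and deviation question is likewise a consequence of the same ambiguity rather than a separate fault.

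**Conclusion.** The inconsistency is real and should be fixed. For an Arm A subject who requires a strong CYP3A inducer on study, the current protocol states both a 200 mg/day maximum and a 400 mg/day instruction, and nothing in it says which governs. This conclusion rests on the wording alone and needs no assumption about pharmacokinetics. The 46% exposure figure assumes dose proportionality, and the RDI values assume the time spent at the higher dose. The number of subjects affected is not given and is expected to be small. No effect on the primary PFS analysis, the error rate or the analysis populations is shown. The stake is consistent handling of an individual subject.

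**What to change.** The sponsor should reconcile Sections 6.2.4 and 6.3.2 so that one statement governs a subject who requires a strong CYP3A inducer. The revised text should:

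- say whether the 6.2.4 maximum applies to all dosing or only to re-escalation after a toxicity reduction;
- cross-reference the two sections;
- state whether the resulting dose counts as a protocol deviation or as an overdose under Section 7.2.2.6.

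Which dose rule applies is for the sponsor to decide, and none is proposed here. A protocol clarification letter or a short amendment would be enough. There is no statistical cost.
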